8.2.5.1. Overview of Planned Clinical Laboratory Safety Analyses

Table 13 provides an overview of the planned clinical laboratory safety analyses.

Table 13	Overview of Planned Clinical Laboratory Safety Analyses
----------	---

	Absolute				Change from Baseline			
Parameter	Summary		Individual		Summary		Individual	
	Т	F	F	L	Т	F	F	L
Chemistry								
Chemistry Values by	Y				Y			
Visit								
Worst Case Chemistry Results by PCI Criteria Post-Baseline Relative to Baseline	Y							

200807

	Absolute				Change from Baseline				
Parameter	Summary		Individual		Summary			vidual	
-	Т	F	F	L	Т	F	F	L	
Hematology									
Hematology Values by Visit	Y				Y				
Worst Case									
Hematology Results by									
PCI Criteria Post-	Y								
Baseline Relative to									
Baseline									
Other Laboratory Tests									
Other Laboratory	Y				Y				
Values by Visit					1				
Worst Case Other									
Laboratory Results by									
PCI Criteria Post-	Y								
Baseline Relative to									
Baseline									
Hepatobiliary (Liver)								1	
Liver	N/								
Monitoring/Stopping Event Reporting	Y								
Hepatobiliary									
Laboratory	Y								
Abnormalities									
Medical Conditions for									
Subjects with Liver				Y					
Stopping Events									
Substance Use for				Y					
Subjects with Liver				Ŷ					
Stopping Events Scatter Plot of									
Maximum vs. Baseline		Y							
for ALT		I							
Scatter Plot of									
Maximum ALT vs.		V							
Maximum Total		Y							
Bilirubin									
All Laboratory									
All Laboratory Data for									
Subjects with Any				Y					
Value of PCI									
All Laboratory Data				Y					
Iron					· · · · ·				
Worst Case Iron									
Results by PCI Criteria				Y					
Post-Baseline Relative									
to Baseline									

200807

NOTES:

- T = Table, F = Figure, L = Listing, Y = Yes display generated.
- Summary = Represents TFL related to any summaries (i.e. descriptive statistics) of the observed raw data.
- Individual = Represents FL related to any displays of individual subject observed raw data.

8.2.5.2. Planned Clinical Laboratory Safety Display Details

Clinical Chemistry

Continuous on-treatment values (see Section 10.4.1) will be summarized using mean, standard deviation, minimum, P25, median, P75, and maximum for each scheduled visit and for baseline and end of treatment (see Section 10.6.4) by treatment group..

Continuous on-treatment change from baseline values will be summarized using mean, standard deviation, minimum, P25, median, P75, and maximum for each scheduled visit and for end of treatment (see Section 10.6.4) by treatment group.

The number and percentage of subjects with on-treatment or worst case laboratory results relative to PCI criteria (see Section 10.8.1) which are post-baseline relative to baseline will be summarized by laboratory test, category and treatment group. See Section 10.6.4 for additional information on worst case values and PCI categories.

Hematology

The displays presented for clinical chemistry laboratory values will also be presented for the hematology laboratory tests listed in Section 8.2.5.

Other Laboratory Tests

The displays presented for clinical chemistry laboratory values will also be presented for the other laboratory tests listed in Section 8.2.5.

On-treatment hsCRP values will be log-transformed (see Section 10.5.2) and summarized using geometric mean, coefficient of variation, minimum, P25, median, P75, and maximum for each scheduled visit by treatment group.

Percent change from baseline in log-transformed (see Section 10.5.2) on-treatment hsCRP values will be summarized using geometric mean, 95% confidence interval, minimum, P25, median, P75, and maximum for each scheduled visit by treatment group.

Hepatobiliary (Liver)

Please refer to the protocol for details of liver chemistry stopping criteria.

Liver monitoring/stopping events will be summarized by treatment group.

Hepatobiliary laboratory abnormalities will be summarized by treatment group.

Medical conditions for subjects with liver stopping events and substance use for subjects with liver stopping events will be listed.

200807

A scatter plot of maximum on-treatment ALT values versus baseline ALT values will be produced.

A scatter plot of maximum on-treatment total bilirubin (xULN) versus maximum on-treatment ALT (xULN) values will be produced.

All Laboratory

A listing of all laboratory data for subjects with on-treatment laboratory values outside of PCI criteria will be provided.

A listing of all laboratory data will be provided.

Iron parameters

The number and percentage of subjects with on-treatment or post-treatment worst case laboratory results relative to PCI criteria (see Section 10.8.1) which are post-baseline relative to baseline will be summarized by laboratory test, category and treatment group. See Section 10.6.4 for additional information on worst case values and PCI categories.

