10.2.1.3. Schedule of Assessments for Subjects Permanently Discontinuing Randomized Treatment

Protocol Activity All assessments pre-dialysis unless otherwise specified	Early Treatment Discontinuation	Day 1 through Week 52 ⁷			
(Note: All visit timings are relative to Day 1)	Visit (within 2 weeks of discontinuing randomized treatment)	Week 4, 16, 28, 40, 52 ± 2 weeks	Unscheduled		
IRT system transaction	Х				
SBP/DBP, HR (pre- and post-dialysis for in-center HD subjects; between treatments for HHD; at study visits per standard of care for PD) (single readings unless otherwise indicated)	X (triplicate)	x	Х		
ECG	Х				
Iron therapy, transfusions ¹	Х	Х	Х		
Serum pregnancy test (FRP only)	Xe				
HemoCue Hgb	Х	Х	Х		
Hematology ³ ,	Х	Х			
Clinical chemistry ³	Х	Х			
Ferritin, total iron, UIBC, hepcidin, lipids, iPTH	Х				
Hospitalization ¹ , kidney transplant ¹	Х	Х	Х		
Non-serious AEs, AEs of special interest, SAEs, clinical events	Х	Х	Х		
Review concomitant medications	Х	Х	Х		
Healthcare resource utilization (subject reported)	Х				
PGI-S, PGI-C ^{4, 9}	Х				
SF-36 ^{4, 9}	Х				
EQ-5D-5L& EQ-VAS ^{4, 5, 9}	Х				
ABPM sub-study (Appendix 12): 24 hour ABPM		X (Week 16)			
Record awake and sleep times		X (Week 16) ²			

Note: see footnotes on next page

200807

Schedule of Assessments for Subjects Permanently Discontinuing Randomized Treatment (Continued)

Protocol activity (visits ± 2 week)		Yea	r 2 7			Yea	r 3 ⁷				Year 47				
(Note: All visit timings are relative to Day 1)	Week 64	Week 76	Week 88	Week 100	Week 112	Week 124	Week 136	Week 148	Week 160	Week 172	Week 184	Week 196	Week 208	Unscheduled	End of Study ⁸
IRT system call															Х
SBP/DBP, HR (pre- and post- dialysis for in-center HD subjects, between treatments for HHD and PD subjects) (single readings unless otherwise indicated)	х	х	х	х	х	х	х	х	х	х	х	х	х	х	Х
HemoCue Hgb	Х	Х	Х	Х	Х	Х	Х	Х	Х	Х	Х	Х	Х	Х	
Hematology ³	Х	Hgb only	Х	Hgb only	Х	Hgb only	Х	Hgb only	Х	Hgb only	Х	Hgb only	Х		Х
Clinical chemistry ³	Х		Х		Х		Х		Х		Х		Х		Х
Hospitalization ¹ , kidney transplant ¹	Х	Х	Х	Х	Х	Х	Х	Х	Х	Х	Х	Х	Х	Х	Х
Non-serious AEs, SAEs, AEs of special interest, clinical events	Х	Х	Х	Х	Х	Х	Х	Х	Х	Х	Х	Х	Х	Х	Х
Review concomitant medications	Х	Х	Х	Х	Х	Х	Х	Х	Х	Х	Х	Х	Х	Х	Х

1. Record in eCRF, if applicable.

2. Subject will record sleep and wake time during the ABPM session.

3. See details on hematology and clinical chemistry in Protocol Section 7.4.11.

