10.4.1.2. Treatment States for CV Endpoint Data

Treatment State	Definition
Pre-Treatment	Date < Treatment Start Date
On-Treatment	Treatment Start Date ≤ Date ≤ Last Non-Zero Dose Date + 28 days
Post-Treatment	Date > Last Non-Zero Dose Date + 28 days
Post-Randomization	Randomization Date \leq Date

NOTES:

 If the last non-zero dose date is missing and the treatment start date is non-missing and Date ≥ Treatment Start Date, then the assessment will be considered to be On-Treatment

• Treatment state definitions use the imputed CV endpoint date

10.4.1.3. Treatment States for BP, Lipid Parameters, Clinical Chemistry, Hematology, Other Laboratory Tests, Hepatobiliary (Liver) and Vital Signs Data

Treatment State	Definition
Pre-Treatment	Date ≤ Treatment Start Date
On-Treatment	Treatment Start Date < Date ≤ Last Non-Zero Dose Date + 1 day
Post-Treatment	Date > Last Non-Zero Dose Date + 1 day
Post-Randomization	Randomization Date < Date

NOTES:

• If the last non-zero dose date is missing and the treatment start date is non-missing and Date > treatment start date, then the assessment will be considered to be On-Treatment

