10.6. Appendix 6: Derived and Transformed Data

10.6.1. General

Multiple Measurements at One Time Point

- Mean of the measurements will be calculated and used in any derivation of summary statistics but if listed, all data will be presented.
 - Triplicate BP and HR measurements are expected at certain time points (See Section 10.2.1)
- Subjects having both High and Low values for Normal Ranges at any post-baseline visits for safety parameters will be counted in both the High and Low categories of "Any visit post-baseline" row of related summary tables. This will also be applicable to relevant Potential Clinical Importance summary tables.

Randomization Date

• Date subject was randomized

Treatment Start Date

• First randomized treatment dose start date

Last Non-Zero Dose Date

- Date of last actual dose of randomized study treatment from the IP Discontinuation eCRF form.
 - The dose steps used by the dosing algorithm described in the protocol include a dose hold or a zero dose. If subjects are assigned by the algorithm to a zero dose, they do not receive randomized treatment for that period. Hence, it would be possible for a subject to complete the study, while still following the dosing algorithm, but not be actually taking any actual randomized treatment. The last non-zero dose date, then captures the latest date in the study that a subject physically took a dose of randomized treatment.
- The eCRF allows for the possibility of partial or missing dates to be recorded for the last actual dose of randomized study treatment on the IP Discontinuation form (i.e., missing day, or day and month, or day and month and year). In such a case, or in case of subjects who have a non-missing treatment start date, but are a missing an IP Discontinuation form, the following conventions will be applied in order to impute a last non-zero dose date:
 - Missing day:
 - The last day of the month will be used, unless the treatment stop date also occurs in the same month; in this case, the treatment stop date will be used.
 - Missing day and month;
 - '31' will be used for the day and 'Dec' will be used for the month, unless the treatment stop date also occurs in the same year; in this case the treatment stop date will be used.
 - Missing day, month, and year:
 - Treatment stop date will be used only for subjects who have a nonmissing treatment start date.

200807

Treatment Stop Date				

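### Both liver scatter plots stop counting one day after the last dose, so in a subject who stops for good a later peak cannot be plotted and a combined elevation can appear as ALT alone

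*SAP*

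**What the plan says.** Section 8.2.5.2 plans two liver scatter plots. The first: "A scatter plot of maximum on-treatment ALT values versus baseline ALT values will be produced". The second: "A scatter plot of maximum on-treatment total bilirubin (xULN) versus maximum on-treatment ALT (xULN) values will be produced". Both rest on the term on-treatment, which the SAP defines by data type.

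The governing table is section 10.4.1.3, "Treatment States for BP, Lipid Parameters, Clinical Chemistry, Hematology, Other Laboratory Tests, Hepatobiliary (Liver) and Vital Signs Data". It sets on-treatment as "Treatment Start Date < Date ≤ Last Non-Zero Dose Date + 1 day" and post-treatment as "Date > Last Non-Zero Dose Date + 1 day". Section 10.6.1 explains the anchor date: "The last non-zero dose date, then captures the latest date in the study that a subject physically took a dose of randomized treatment".

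Chemistry, which under section 8.2.5 includes ALT and bilirubin, continues after treatment stops. Section 10.2.1.3 schedules it at an early treatment discontinuation visit "within 2 weeks of discontinuing randomized treatment" and at later visits to the end of study. Section 10.2.1.1 has a follow-up column with chemistry 4 to 6 weeks after randomized treatment stops.

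Elsewhere in 8.2.5.2, the iron display uses "on-treatment or post-treatment worst case" results, and the vital-sign display in 8.2.6.2 does the same.

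**The concern.** Plotting the maximum bilirubin against the maximum ALT lets a reader see which subjects had both raised, and in which arm. The two peaks need not coincide. If ALT rises first, treatment is stopped and bilirubin rises afterwards, the second peak falls outside the plotting window.

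The truncation can depend on the outcome being displayed. The SAP anticipates liver stopping events and gives them their own table and listings. For such a subject the event ends dosing, and the end of dosing closes the window. Subjects without a liver event carry on contributing samples. The subjects for whom the plot matters most are thus the ones most exposed to the cut.

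At stake is the placement of individual points on a descriptive safety figure. No co-primary or other formal test depends on it.

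**Working it through.** The SAP gives no figure to reproduce on this point. The check is to trace one term to its definition and compare dates.

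**Step 1: which window applies.** Both plots use on-treatment maxima (8.2.5.2). Section 10.4.1.3 names hepatobiliary data. With day 0 as the last non-zero dose date, the window closes at day 0 + 1 = day +1, and day +2 is the first post-treatment day.

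**Step 2: to whom it applies.** The anchor is the last day on which a dose was physically taken. Values drawn during an interruption that is later resumed precede that day and stay on-treatment. The loss concerns permanent stops only. Where the anchor date is missing, 10.4.1.3 treats later values as on-treatment, but 10.6.1 imputes the date, so this will rarely matter.

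**Step 3: what falls outside.** The day counts below assume that stopping coincides with the last non-zero dose.

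| Chemistry after stopping | Days after last dose | Can it set the plotted maximum? |
|---|---|---|
| Early discontinuation visit (10.2.1.3) | 0 to 14 | Only if drawn by day +1 |
| Follow-up visit (10.2.1.1) | 28 to 42 | No |
| Later visits after discontinuation (10.2.1.3) | Depends on when treatment stopped | Only if drawn by day +1 |

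The separate schedule for subjects who discontinue permanently has no follow-up column of its own. For those subjects, the 4-to-6-week sample rests on the general schedule in 10.2.1.1.

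**Step 4: how many on-treatment samples there are.** Scheduled post-baseline chemistry in subjects on treatment falls at Weeks 4, 16, 28, 40 and 52, then Week 64 and every 24 weeks from there (88, 112 and so on). Section 8.2.5 also allows unscheduled and retest samples, which count while dosing continues. Without one, the scheduled sample before the stop may be the only raised value plotted.

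**Step 5: effect on one point.** Assumed values, not from the SAP: on day 0, ALT is 5xULN and bilirubin 1xULN; bilirubin later peaks at 3xULN and ALT does not exceed 5xULN. The day of the peak is varied.

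| Day of bilirubin peak | Plotted now (ALT, bilirubin) | Plotted with a +42 day window |
|---|---|---|
| +1 | (5, 3) | (5, 3) |
| +2 | (5, 1) | (5, 3) |
| +7 | (5, 1) | (5, 3) |
| +14 | (5, 1) | (5, 3) |
| +42 | (5, 1) | (5, 3) |

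The change from (5, 3) to (5, 1) comes from the data filter alone.

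**Step 6: other windows in the SAP.** Cardiovascular endpoints run to last non-zero dose + 28 days (10.4.1.2). Adverse events use + 1 day (10.4.1.4). The iron and vital-sign worst-case displays admit post-treatment values. The SAP gives no reason for the narrower choice in the liver plots.

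**The case against.** The strongest case on the other side is that these are descriptive figures among several liver displays.

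- Section 8.2.5.2 also plans a liver monitoring and stopping event table and a hepatobiliary abnormality table, neither with a stated on-treatment limit.
- Any subject with an on-treatment value outside the clinical-concern limits has all laboratory data listed. Section 10.8.1 sets those limits at 3xULRR or above for ALT and 2xULRR or above for total bilirubin. A subject with on-treatment ALT at or above 3xULRR and a later bilirubin peak is in that listing, and in the listing of all laboratory data.
- The chemistry worst-case summary reads as if post-treatment had dropped out of the sentence, so it may not be cut at + 1 day.
- A one-day limit is usual in this SAP; the 28-day cardiovascular window is the exception.
- Discontinued subjects have chemistry through Week 208 and End of Study, so an unlimited maximum could draw in years of off-drug samples and plot unrelated disease.

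Most of this stands, and it limits the point. A reader might infer that the report will understate hepatotoxicity, or do so unequally between arms. The SAP does not support that: the values are reported elsewhere, no count of affected subjects is given, and nothing shows a difference between arms. A reader might also infer that the abnormality table has the same cut; no window is stated for it. The objection to an unlimited maximum is sound and argues for a bounded window.

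The gap in the figure remains. The ALT-by-bilirubin plot is the only display that the SAP explicitly describes as pairing the two tests by subject. The worst-case summary is by single test, and a listing gives no view across arms.

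**Conclusion.** The point holds in a limited form. By the SAP's own definitions, neither liver scatter plot can show a peak reached two or more days after the last dose in a subject who has permanently stopped, and a combined elevation can plot as ALT alone.

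The size is unknown. It depends on how many subjects stop permanently with a liver abnormality and how often a peak follows the last dose; the SAP gives neither. Misplacement of individual points is certain wherever a late peak exceeds the on-treatment maximum. Understatement between arms is possible, not shown.

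The conclusion assumes that the plots will be programmed to 10.4.1.3 as written and that post-stop chemistry is obtained as scheduled. The liver stopping criteria are left to the protocol and are not judged here. The change is worth making because it removes an outcome-dependent cut at little cost; it does not bear on the co-primary conclusions.

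**What to change.** Keep both on-treatment plots. In 8.2.5.2, either add a second version of each or extend the existing ones, so that maxima include post-treatment ALT and bilirubin over a bounded window that covers the early discontinuation visit and the 4-to-6-week follow-up visit. Last non-zero dose + 42 days is one such window (6 weeks x 7 = 42). The cardiovascular window of + 28 days would take in only the first day of the 28-to-42-day follow-up range. If the plots are extended rather than duplicated, use a distinct symbol for any point with a maximum after last non-zero dose + 1 day, and explain it in a footnote.

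One detail needs settling in the programming specification. The visits are timed from stopping randomized treatment, while the window runs from the last non-zero dose. Where zero-dose periods separate the two dates, the SAP should say which date anchors the window.

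This point requires no change to the hepatobiliary abnormality table.

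The cost is a few lines of SAP text and a changed data filter; the samples are already scheduled. The downside is that a few plotted maxima may reflect causes arising off drug. The symbol or the separate version makes these visible and leaves the on-treatment reading intact.

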8.2.6. Vital Signs Analyses

Vital signs are assessed in this study according to the schedule outlined in the Time and Events table (see Section 10.2.1) and include the following assessments:

- Height
- HR
- Weight
- Estimated Dry Weight

Summaries and analyses of BP values are described in earlier safety sections and will not be included with vital signs summaries. However, BP values will be included in PCI summaries.

The vital signs analyses will be based on the Safety population, unless otherwise specified.

8.2.6.1. Overview of Planned Vital Signs Analyses

Table 14 provides an overview of the planned vital signs analyses.

200807

	Absolute				Change from Baseline			
Parameter	Summary		Individual		Summary		Individual	
	Т	F	F	L	Т	F	F	L
Vital Signs								
Vital Signs by Visit	Y				Y			
Summary of Worst								
Case Vital Signs	Y							
Results by PCI Criteria								
All Vital Signs for								
Subjects with Any				v				
Value of Potential				ľ				
Clinical Importance								

Table 14 **Overview of Planned Vital Signs Analyses**

NOTES:

- T = Table, F = Figure, L = Listing, Y = Yes display generated.
- Summary = Represents TFL related to any summaries (i.e. descriptive statistics) of the observed raw data.
- Individual = Represents FL related to any displays of individual subject observed raw data.

8.2.6.2. **Planned Vital Signs Display Details**

Vital sign values will be summarized using mean, standard deviation, minimum, P25, median, P75, and maximum for each scheduled visit and for baseline and end of treatment by treatment group.

Vital sign change from baseline values will be summarized using mean, standard deviation, minimum, P25, median, P75, and maximum for each scheduled visit and for end of treatment by treatment group.

The number and percentage of subjects with on-treatment or post-treatment worst case vital sign results relative to PCI criteria (see Section 10.8.1) which are post-baseline relative to baseline will be summarized by test, category and treatment group. See Section 10.6.4 for additional information on worst case values and PCI categories. The difference between on-treatment post-dialysis weight and estimated dry weight will be summarized using mean, standard deviation, minimum, P25, median, P75, and maximum for each scheduled visit and for baseline and end of treatment by treatment group. A corresponding line plot will be provided to display this data graphically.

A listing of all vital signs data for subjects with on-treatment vital signs values outside of PCI criteria will be provided.

8.2.7. Electrocardiograms

Electrocardiograms (ECGs) will be read locally and ECG data will not be included in summary tables or individual subject listings.

8.2.8. Pregnancies

A listing of all subjects who became pregnant during the study will be included.

200807

8.2.9. Other Safety Analyses

Clopidogrel Analyses

The following analyses will be conducted to confirm the effect of clopidogrel coadministration.

The treatment emergent AEs and SAEs will be summarized with the number, percentage and rate per 100 person-years, by clopidogrel co-administration, treatment group, and system organ class and preferred term. Clopidogrel co-administration is defined as subjects who use clopidogrel once or more during the on-treatment state for concomitant medications (see Section 10.4.1).

The number and percentage of subjects with a >1 g/dL increase in Hgb over 2 weeks (assessed at Week 2 and Week 4), or a >2 g/dL increase in Hgb within any 4-week period from Week 4 to Week 52, will be summarized by visit by clopidogrel co-administration, and by treatment group using HemoCue Hgb values. This summary will be presented using evaluable Hgb values only (see Section 10.6.3).

The number and percentage of subjects with a >2 g/dL increase in Hgb within any 4week period from Week 4 to Week 52, will be summarized by visit by clopidogrel coadministration, and by treatment group using central laboratory Hgb values. This summary will be presented using evaluable Hgb values only (see Section 10.6.3).

For the above two tables, the Clopidogrel co-administration groups are baseline clopidogrel users, new clopidogrel users, and clopidogrel non-users during the first year of the study. Baseline clopidogrel users, defined as subjects who use clopidogrel at randomization, will be summarized only at Week 2 and Week 4 for the HemoCue Hgb table, and only at week 4 in the central laboratory Hgb table. New clopidogrel users are defined as subjects who started clopidogrel after randomization during the on-treatment state for concomitant medications (see Section 10.4.1) in the first year of the study. If they started clopidogrel within two weeks of a scheduled visit (i.e. visit date - 2w < clopidogrel start date \leq visit date + 2w), they will only be summarized in the following scheduled visit. Clopidogrel non-users are subjects who do not use clopidogrel neither at randomization nor anytime during the on-treatment state for concomitant medications (see Section 10.4.1) in the first year of the study.

The number and percentage of subjects with a Hgb value ≥ 12 g/dL during the study will be summarized by clopidogrel co-administration, and by treatment group using evaluable Hgb values (see Section 10.6.3). Clopidogrel co-administration is defined as subjects who use clopidogrel once or more either at randomization or during the on-treatment state for concomitant medications (see Section 10.4.1).

The number and percentage of subjects who had dose adjustments (decreases, increases, no change) will be summarized at Week 2 and Week 4 by baseline clopidogrel coadministration, and by treatment group. The number of dose decreases per subject will be summarized for baseline clopidogrel users, using mean, standard deviation, minimum, P25, median, P75, and maximum by baseline clopidogrel use, and by treatment group, for

200807

Day 1 to Week 12. Baseline clopidogrel co-administration is defined as subjects who use clopidogrel at randomization.

The number and percentage of subjects had dose adjustments (decreases, increases, no change) will be summarized for new clopidogrel users, who started clopidogrel after randomization, during the on-treatment state for concomitant medications (see Section 10.4.1), by treatment group. If they started clopidogrel within two weeks of a scheduled visit (i.e. visit date - 2w < clopidogrel start date \leq visit date + 2w), they will be summarized in the following scheduled visit. The number of dose decreases per subject will also be summarized for these new clopidogrel users using mean, standard deviation, minimum, P25, median, P75, and maximum by clopidogrel use, and by treatment group, for clopidogrel use start date to clopidogrel use + Week 12.

The median assigned dose by treatment, by clopidogrel co-administration, and visit will be displayed graphically for each scheduled study visit from day 1 to week 52 using a line plot. The line plot of median assigned dose along with the first and the third quartiles by time will include vertical reference lines to identify the EP as well as the number of subjects by treatment group contributing to each median value. This plot will be created by treatment group separately for subjects receiving epoetin alfa and darbepoetin alfa and these plots will also be overlaid on a graph of corresponding mean evaluable Hgb values by visit. Since it is possible for subjects to switch from epoetin alfa to darbepoetin alfa during the study, subjects who receive both treatments during the study will be counted in each group. Clopidogrel co-administration here is defined as subjects who use clopidogrel once or more, at randomization, or during the on-treatment state for concomitant medications (see Section 10.4.1) in the first year of the study.

A box plot of evaluable Hgb change at Week 2 from baseline, by baseline clopidogrel coadministration and treatment group will be produced. Hemocue Hgb will be used in this figure, since only Hemocue Hgb is available at Week 2. Baseline clopidogrel coadministration is defined as subjects who use clopidogrel at randomization. This box plot will be repeated at Week 4 using evaluable Hgb, by baseline clopidogrel coadministration and treatment group.

A box plot of 4-week changes in evaluable Hgb after starting clopidogrel will also be produced by treatment for new clopidogrel users, who started clopidogrel after randomization, during the on-treatment state for concomitant medications (see Section 10.4.1). The 4-week change in evaluable Hgb will be estimated by calculating the change at the first visit after starting clopidogrel, from the previous visit at least 4 weeks before. The first visit after starting clopidogrel is defined as the first visit (scheduled or unscheduled) after clopidogrel start that was at least two weeks after the start date of clopidogrel.

COVID-19 Analyses

The following COVID-19 related displays will be provided.

A summary of the number and percentage of subjects for the following assessments will be produced: Case Diagnosis, COVID-19 Test performed, and Results of the COVID-19 test.

Summaries of characteristics of COVID-19 AEs will include the number, percentage of subjects having at least one occurrence, the outcome, maximum intensity, and the duration of the AE summarized by treatment group. For each count, a subject will be summarized as follows:

- Outcome: The subject will be counted within a category if there is at least one specific AE in that category.
- Maximum intensity: The specific AE with the maximum intensity will be counted for this purpose. For example, a subject will be counted in the 'severe' category if there is at least one specific AE with severe intensity. A subject will be counted in the 'moderate' category if there is at least one specific AE with moderate intensity and there is no specific AE with severe intensity.
- Duration of the occurrence (days): AE resolution date AE onset date/AE worsening date + 1 for the occurrence

A summary of the number and percentage of subjects with COVID-19 symptoms will be produced.

A summary of exposure adjusted incidence rates over time (see Section 10.6.4) will be produced by treatment group for any treatment emergent AE, any treatment emergent SAE, and any treatment emergent Severe AE, for two periods – pre COVID-19 pandemic and during COVID-19 pandemic. The summary will be produced overall, by Country, Region, Sex, and by Age at randomization (Grouping 2) (see Section 10.10.1). A summary of exposure adjusted incidence rates by treatment group will also be produced for Common (>5%) AEs for two periods – pre COVID-19 pandemic and during COVID-19 pandemic.

